4 STUDY OBJECTIVES

4.1 Primary Objective

To evaluate the impact of smart adherence technology for monitoring of LUM/IVA adherence rates among subjects 16 years of age and older with CF who are homozygous for the *F508del-CFTR* mutation

4.2 Secondary Objectives

To collect subject and physician feedback on the use of smart adherence technology to monitor LUM/IVA adherence

4.3 Other Objectives

Not applicable

5 STUDY ENDPOINTS

5.1 Adherence Endpoint

This study was terminated early by a business decision. The data collected at the time of termination are limited and premature due to early termination. Therefore, the planned adherence endpoints listed in Sections 2 and 7 of the protocol will not be performed. Based on the expected available data, a list of applicable adherence endpoints below will be analyzed as follows:

- Mean percentage adherence to LUM/IVA treatment over any treatment duration for all subjects.
- Mean percentage adherence to LUM/IVA treatment over 0 through 12 weeks for subjects who have at least 12 weeks of eligible smart pill bottle data.

- Proportion of subjects with $\geq 80\%$ adherence over 0 through 12 weeks for subjects who have at least 12 weeks of eligible smart pill bottle data
- Proportion of subjects with $\geq 90\%$ adherence over 0 through 12 weeks for subjects who have at least 12 weeks of eligible smart pill bottle data

6 STUDY DESIGN

This is a Phase 4, open-label, randomized, multicenter, 2-arm, parallel-group pilot study evaluating LUM/IVA adherence. Each study arm will use a smart technology with either active or inactive dosing alert features.

This study includes:

- Screening Period (Day -28 through Day -1)
- Treatment Period (Day 1 through Week 48)
- Safety Follow-Up Visit (28 [± 7] days after the final dose of study drug). Subjects who begin commercially available LUM/IVA combination therapy within 28 (± 7) days of the last dose of LUM/IVA do not have to complete the Safety Follow-up Visit.

[Figure6-1](#) depicts a schematic of the study design. Approximately 75 subjects will be enrolled in this study. All subjects will receive LUM 400 mg/IVA 250 mg every 12 hours (q12h) through Week 48.

[figure not shown]
Randomization of subjects to the 2 study arms will be stratified by age (<23 versus ≥ 23 years of age) and forced expiratory volume in 1 second (FEV₁) severity ($<70\%$ versus $\geq 70\%$ predicted) at the Screening Visit. All subjects will be randomized at 2:1 ratio to 1 of the following 2 smart adherence technology study arms:

- **Study Arm A:** Smart Pill Bottle, activated
- **Study Arm B:** Smart Pill Bottle (control), de-activated alerts and feedback features

Subjects will receive standardized education on the benefit of medication adherence and training on the use of the assigned smart adherence technology. During applicable study visits, subjects will complete adherence and technology satisfaction assessments; and physicians will complete technology satisfaction assessments at Week 48. Tables 11-1 and 11-2 in Appendix A provide a list of assessments by study visit.

All subjects will be required to complete study assessments for all scheduled visits. Subjects who prematurely discontinue study drug treatment will complete a Safety Follow-up Visit.

Figure 6-1 Study Design

- All subjects start treatment with lumacaftor/ivacaftor on Day 1.
- Safety Follow-up visit is required only for subjects who do not begin commercially available LUM/IVA within 28 (\pm 7) days of last dose of study drug.

6.1 Sample Size and Power

A total of approximately 75 subjects were to be enrolled and randomized at 2:1 ratio to 1 of 2 study arms: Smart Pill Bottle (Study Arm A) and Smart Pill Bottle (control) de-activated alerts and feedback features (Study Arm B, control arm), resulting in approximately 50 subjects in the intervention arm and approximately 25 subjects in the control arm.

The primary endpoint is the mean percentage adherence to LUM/IVA treatment over 48 weeks. Assuming a standard deviation (SD) of 8, a sample size of 50 in the intervention arm and 25 in the control arm will have 80% power to detect a difference of 5.6% between the means for the 2 arms using a 2-sided, 2-sample *t*-test at the 5% significant level.

Data from studies VX09-809-102, VX12-809-103, and VX12-809-104 were used for this sample size calculation. Sample sizes based on a range of SDs [REDACTED].

6.2 Randomization

Randomization of subjects to the 2 study arms will be stratified by age (<23 versus \geq 23 years of age) and forced expiratory volume in 1 second (FEV₁) severity (<70% versus \geq 70% predicted) determined at the Screening Visit. All subjects will be randomized at 2:1 ratio to 1 of the following 2 smart adherence technology study arms:

- **Study Arm A:** Smart Pill Bottle, activated
- **Study Arm B:** Smart Pill Bottle (control), de-activated alerts and feedback features

An interactive web response system (IWRS) will be used to assign subjects to study arms using a list of randomization codes generated by a designated vendor.

6.3 Blinding and Unblinding

This is a study of adherence with a deactivated smart adherence technology as the control arm. LUM/IVA treatment is given open-label to all subjects.

7 ANALYSIS SETS

The following analysis sets are defined: Full Analysis Set (FAS), and Safety Set.

The **All Subjects Set** is defined as all subjects who have been randomized or have received at least one dose of study drug. This analysis set will be used for all individual subject data listings and the disposition summary table, unless specified otherwise.

The **Full Analysis Set (FAS)** will include all randomized subjects who received at least 1 dose of LUM/IVA. The FAS will be used for all analyses except the safety analyses in this study. Given the nature and objective of this study, the subjects will be grouped and analyzed according to the smart technology arm that they actually received and not according to the arm that they were randomized to.

The **Safety Set** will include all subjects who received at least 1 dose of LUM/IVA. The Safety Set will be used for all safety analyses.

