**Table 8-1 Study VX15-809-114 Smart Adherence Technology Study Arms**

Smart Adherence Technology	Activated Features	Access to LUM/IVA Compliance Status	Number (n)
Smart Pill Bottle (Study Arm A)	Real-time dosing data transfer, electronic medication reminders/missed dose alerts (audio, visuals, texts, emails, phone calls)	Site staff and physicians, CRO, Vertex	50
Smart Pill Bottle, Control (Study Arm B)	Real-time dosing data transfer to CRO/Vertex only	CRO/Vertex only	25

CRO: contract research organization

The use of active smart adherence technologies (smart pill bottles) will provide subjects with objective and real-time feedback on dosing adherence, including reminders of upcoming or missed doses. Study physicians will access dosing adherence data and review them with subjects in Study Arm A at scheduled study visits. Subjects in Study Arm B will not receive any alerts, reminders, or real-time feedback on dosing adherence. Study Arm B will provide objective data on dosing adherence without influencing subjects to take a scheduled dose of LUM/IVA.

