## 12.2 Analysis Sets

The Full Analysis Set (FAS) will include all randomized subjects who received at least 1 dose of LUM/IVA. The FAS will be used for all analyses in this study.

The Safety Set will include all subjects who received at least 1 dose of LUM/IVA. The Safety Set will be used for all safety analyses, unless otherwise specified.

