Malfunction of smart bottle: any subject who got a smart bottle with a malfunction signal and never received the alerts who was subsequently switched to the control (Arm B) will be considered as a control subject (Arm B).

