8.2 Background Characteristics

8.2.1 Subject Disposition

The number of subjects in the following categories will be summarized overall and by study arm:

- Randomized
- Safety Set
- Full Analysis Set (FAS)

The number and percentage (based on FAS) of subjects in each of the following disposition categories will be summarized overall and by study arm:

- Completed study drug
- Prematurely discontinued study drug and the reason for discontinuation
- Completed study (defined as completed the planned study treatment and Safety Follow-up Visit)
- Prematurely discontinued the study and the reason for discontinuation

A listing will be provided for subjects who discontinued treatment or who discontinued study, along with reasons for discontinuations.

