8.3.2 Analysis of Adherence Endpoints

Mean percentage adherence to LUM/IVA treatment over treatment duration for all subjects

The percentage adherence over treatment duration for each subject is defined as:

$$100 \times (\text{total number of smart bottle openings over the eligible treatment duration excluding the physician-directed interruption periods of the eligible treatment duration}) / [2 \times (\text{eligible duration of treatment} - \text{the number of physician-directed interruption days of the eligible treatment duration})]$$

Note: (1) the physician-directed interruption is defined as the reported interruptions due to reasons not being “Non-compliance”; (2) if there are more than 2 smart bottle openings at any day, they will be counted as 2 in calculation of the adherence endpoints. (3) the eligible treatment duration = eligible date of last dose – date of first dose + 1, where the eligible date of last dose is defined to be either the CRF collected date of last dose or the last activity date of smart bottle data, whichever is earlier.

Descriptive statistics will be provided by the number of subjects (n), mean, SD, SE, median, min, and max by treatment arm based on FAS. [REDACTED]

The percentage adherence will also be listed.

Mean percentage adherence to LUM/IVA treatment over 0 through 12 weeks for subjects who have at least 12 weeks of eligible smart pill bottle data

Subjects who have at least 12 weeks of eligible smart pill bottle data are defined as those who have at least 12 weeks of eligible treatment duration = eligible date of last dose – date of first dose + 1, where the eligible date of last dose is defined to be either the CRF collected date of last dose or the last activity date of smart bottle data, whichever is earlier.

The percentage adherence over 12 weeks for each eligible subject is defined as:

$$100 \times (\text{total number of smart bottle openings over the first 12 weeks excluding the physician-directed interruption periods of the first 12 weeks}) / [2 \times (12 \text{ weeks (ie, 84 days)} - \text{the number of physician-directed interruption days of the first 12 weeks})]$$

Note: (1) the physician-directed interruption is defined as the reported interruptions due to reasons not being “Non-compliance”; (2) if there are more than 2 smart bottle openings at any day, they will be counted as 2 in calculation of the adherence endpoints.

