Descriptive statistics will be provided by the number of subjects (n), mean, SD, SE, median, min, and max by treatment arm based on FAS. [REDACTED]

The percentage adherence will also be listed.

In addition, the number of smart bottle openings during the physician-directed interruption periods will be presented in a by-subject listing. Please note that if there are more than 2 smart bottle openings at any day, they will be counted as the actual number in this listing.

Further exploratory analyses may be performed if deemed necessary and sufficient data is available.

Proportion of subjects with $\geq 80\%$ (or 90%) adherence 0 through 12 weeks for subjects who have at least 12 weeks of eligible smart pill bottle data

For each eligible subject, the percentage of adherence over 12 weeks will be calculated as described above. The proportion of subjects with $\geq 80\%$ adherence rate over 12 weeks and the proportion of subjects with $\geq 90\%$ adherence rate over 12 weeks will be presented in a summary table.

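### The SAP groups adherence by bottle received and, in the visible text, never by randomised arm, so the by-arm means stop comparing the randomised groups if any subject changed arm (minor)

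*SAP*

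**What the plan says.** SAP 7 defines the FAS as randomised subjects who took at least one dose, and uses it for everything except safety. Citing only the nature and objective of the study, it then says that its subjects are "analyzed according to the smart technology arm that they actually received and not according to the arm that they were randomized to".

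SAP 8.1 has a specific rule for device failure. Where the bottle malfunctioned, a subject who "never received the alerts who was subsequently switched to the control (Arm B) will be considered as a control subject".

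The protocol describes alerts as a feature of Arm A. In the text under its Table 8-1, "Subjects in Study Arm B will not receive any alerts, reminders, or real-time feedback on dosing adherence". Protocol 12.2 defines the FAS in the same way and says "The FAS will be used for all analyses in this study", but it gives no grouping rule of either kind.

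SAP 8.3.2 applies the FAS to both mean-adherence summaries: "Descriptive statistics will be provided by the number of subjects (n), mean, SD, SE, median, min, and max by treatment arm based on FAS". In both places, what follows that sentence is redacted. The 12-week endpoints are further limited to "those who have at least 12 weeks of eligible treatment duration". For the two proportions, the SAP says only that the "adherence rate over 12 weeks will be presented in a summary table", without saying whether the table is by arm.

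For disposition, SAP 8.2.1 says "The number of subjects in the following categories will be summarized overall and by study arm", and the categories are randomised, Safety Set and FAS.

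**The concern.** The primary objective concerns the impact of the smart technology on adherence. After early termination, the by-arm bottle means bear on it most directly. Randomisation, stratified by age and FEV1, is what makes the two arms comparable. Grouping by bottle received gives that up for any subject whose arm changed.

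Three features make the malfunction rule more than a formality.

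- **It runs one way.** Only Arm A has alerts that can fail, so this rule can only take subjects out of A and put them into B. The general rule in SAP 7 could in principle move subjects in either direction.
- **It depends on what happened after randomisation:** a malfunction signal, no alerts, then a switch. The visible text does not say how the switch is decided.
- **The bottle both delivers the intervention and measures the outcome,** because adherence is counted from recorded openings. A malfunction is therefore not obviously neutral to recorded adherence, although nothing in the documents shows that it affects it.

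Moved subjects may also differ from the other controls in what they were given. Protocol 10.1.2 gives Arm A additional instruction on the activated features, and Protocol 11.3.1 has only Arm A review data with physicians. The SAP 8.1 rule looks only at alerts and the switch.

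At stake is the reading of a between-arm difference. Tablet-count and interruption-day compliance (SAP 8.2.6) gives no independent check on grouping, because it uses the same FAS.

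**Working it through.** **Plan's own figure.** SAP 6.1 states 80% power for a 5.6-point difference with 50 and 25 subjects, SD 8 and two-sided 5%. The standard error of the contrast is 8 × √(1/50 + 1/25) = 1.96, and 5.6/1.96 = 2.86. The noncentral t with 73 degrees of freedom gives power 0.805, so the figure is reproduced. The point does not depend on it, but it supplies the scale: a standard error of about 2.0 and a target of 5.6.

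**Inputs.** The 50/25 split and SD 8 come from SAP 6.1. The number of movers k, how their adherence differs from the rest, and the final arm sizes are not in the documents, so everything on these below is an assumption.

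**Case 1: nobody moved.** The two groupings are identical and the shift is 0.

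**Case 2: movers are unrelated to adherence.** The expected shift is 0. For the chance spread, let Ā be the mean of the 50 - k subjects who stay in A, M̄ the mean of the k movers, and B̄ the mean of the 25 randomised to B. The as-received contrast minus the as-randomised contrast is

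(k/50)·Ā - k·[1/50 + 1/(25+k)]·M̄ + [k/(25+k)]·B̄

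with variance 64 × { (k/50)²/(50-k) + k·[1/50 + 1/(25+k)]² + [k/(25+k)]²/25 }.

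- k = 1: 64 × (0.00001 + 0.00342 + 0.00006) = 0.22, so SD about 0.5 points.
- k = 5: 64 × (0.00022 + 0.01422 + 0.00111) = 1.00, so SD about 1.0 point.

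Both are small against the standard error of about 2.0.

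**Case 3: movers differ.** Assume no true effect, both arms averaging 85% as randomised, no openings lost to malfunction, and k movers from A to B at adherence m. Then

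A - B as received = k × (85 - m) × [1/(50-k) + 1/(25+k)].

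| Movers | 15 points lower (m = 70) | 10 points higher (m = 95) |
|---|---|---|
| 1 | 15 × (1/49 + 1/26) = +0.88 | -10 × (1/49 + 1/26) = -0.59 |
| 3 | 45 × (1/47 + 1/28) = +2.56 | -30 × (1/47 + 1/28) = -1.71 |
| 5 | 75 × (1/45 + 1/30) = +4.17 | -50 × (1/45 + 1/30) = -2.78 |

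The as-randomised difference is 0 here because the inputs set it to 0. That is not evidence that as-randomised grouping is free of bias. Against SD 8, the assumed movers lie 15/8 = 1.9 SD below or 10/8 = 1.25 SD above the average, so the larger entries need strong selection.

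**Cost of the randomised grouping.** If alerts truly add 5.6 points and k of 50 Arm A subjects never received them, the as-randomised difference is 5.6 × 49/50 = 5.49 for k = 1 and 5.6 × 45/50 = 5.04 for k = 5. With movers of average adherence, as-received grouping would keep 5.6.

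**The case against.** The strongest case for the SAP is that its choice is open and describes exposure. The malfunction rule covers subjects who never received an alert and were then switched, so calling them controls says what they actually had. Protocol 12.2 states no grouping rule, and the protocol leaves analysis details to the SAP, so the two do not conflict. The study stopped early, the summaries are descriptive, and no between-arm test or estimate is visible. This stands, and it is why the point is minor. It justifies showing an as-received table, but not omitting the randomised one. A reader will still set two by-arm means from a randomised study side by side.

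Other objections also have weight. The redacted text in SAP 8.3.2 could hold a further summary, and the same section allows exploratory analyses. The point is therefore limited to the visible plan. Nothing links malfunction to adherence, and if the two are unrelated the expected shift is zero.

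A reader might infer more than the documents support in three ways:

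- **That subjects did move, because the malfunction rule is so specific.** It is worded as a contingency and reports no case.
- **That the planned output would hide any movement.** SAP 8.2.1 tabulates both randomised and FAS counts by arm, and SAP 8.3.2 lists adherence by subject. Movement might show as a mismatch between rows if the randomised row uses the randomised arm, which is not stated. Undosed subjects could produce the same mismatch. The accurate statement is that no category directly counts subjects analysed outside their randomised arm.
- **That randomised grouping removes all bias.** If a malfunction lost openings, that loss would stay in Arm A. For example, 5 of 50 subjects each losing 15 recorded points (an assumption) would lower the Arm A mean by 5 × 15/50 = 1.5 points.

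**Conclusion.** The point holds in conditional form. The visible SAP summarises adherence only by arm received. If any subject's received and randomised arms differ, the by-arm means are no longer a comparison of the randomised groups. A flat statement that these means are not a randomised comparison would go too far, because the groupings coincide if nobody moved.

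The size and direction of any shift are unknown. It is zero with no movers. It is zero in expectation, with a chance spread of about 0.5 to 1.0 points for 1 to 5 movers, if movers are unrelated to adherence. Under the assumed scenarios at 50/25 it runs from +4.2 to -2.8 points, against a planned detectable difference of 5.6. Final arm sizes are not given, and each mover would weigh more in smaller arms.

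Both mean-adherence endpoints are affected. The 80% and 90% proportions are affected only if they are shown by arm. The harm is a possibly misleading descriptive contrast and not an inflated type I error. This is a cheap improvement of minor severity.

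**What to change.** - **SAP 7 and 8.3.2:** present the by-arm adherence summaries by randomised arm, without the SAP 8.1 malfunction reassignment. This covers both mean endpoints, and the two proportions if they are shown by arm. Keep the as-received version as a labelled supportive table.
- **SAP 8.2.1:** add a count of subjects whose received arm differs from their randomised arm, with a listing of those subjects.
- **Notes to the adherence table:** say that openings lost to a malfunction would lower recorded adherence in the randomised arm. Say also that the 12-week endpoints remain limited to subjects with at least 12 weeks of eligible bottle data. That is a selection made after randomisation, so regrouping alone does not make them fully randomised comparisons.

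The cost is some SAP wording, one extra table, one count and one listing. The statistical price is the slight dilution shown above: a real 5.6-point effect becomes about 5.5 if 1 of 50 Arm A subjects was never alerted, and about 5.0 if 5 of 50 were not. If nobody moved, the two tables agree and the count of zero says so.

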8 STATISTICAL ANALYSIS

8.1 General Considerations

The Schedule of Assessments is provided in [Appendix A](#).

Continuous variables will be summarized using the following descriptive summary statistics: the number of subjects (n), mean, standard deviation (SD), standard error (SE), median, minimum value (min), and maximum value (max).

Categorical variables will be summarized using counts and percentages.

Baseline value, unless specified otherwise, will be defined as the most recent non-missing measurement (scheduled or unscheduled) collected before the first dose of study drug.

Change (absolute change) from baseline will be calculated as postbaseline value minus baseline value

Treatment-emergent (TE) Period will be from the first dose date of the study drug to the Safety Follow-up Visit or 28 days after the last dose, whichever is latest. The TE period will be used for safety analyses.

Unscheduled visits: Unscheduled visit measurements will be included in analysis as follows:

- In scheduled visit windows per specified visit windowing rules.
- In the derivation of baseline/last on-treatment measurements.
- In the derivation of maximum/minimum on-treatment values and maximum/minimum change from baseline values for safety analyses.
- In individual subject data listings as appropriate.

Visit windowing rules: Day 1 is defined as the day of first dose of study treatment. Relative days after Day 1 are calculated as (assessment date – Day 1 date) + 1. Relative days prior to Day 1 are calculated as (assessment date – Day 1 date). The day prior to Day 1 is Day -1. The analysis visit windows for protocol-defined visits are provided in [Appendix B](#). Visit window rules will not apply to the smart technology-reported adherence, which will be collected and stored daily and will be summarized at actual date. Visit window rules will apply to other visit-dependent assessments, including liver function tests, and patient-reported, as well as, physician-reported outcomes.

Incomplete/missing data will not be imputed, unless specified otherwise.

Outliers: No formal statistical analyses will be performed to detect or remedy the presence of statistical outliers, unless specified otherwise.

Multiplicity: No multiplicity adjustment will be performed for hypothesis testing.

Malfunction of smart bottle: any subject who got a smart bottle with a malfunction signal and never received the alerts who was subsequently switched to the control (Arm B) will be considered as a control subject (Arm B).

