#### Smart Pill Bottles

Subjects will be trained to use the smart pill bottle. Subjects in Study Arm A will receive additional instruction on the activated smart pill bottle monitoring features. A site pharmacist will repackage 3 months supply of LUM/IVA from blister packs into 4 Smart Pill Bottles. Three bottles will each store a 1-month supply of LUM/IVA. A fourth bottle will store an additional 7 days supply of LUM/IVA. Only 1 bottle will be activated at a time.

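### The SAP adherence formulas score a day when the bottle did not record, if recording later resumes, as two missed doses

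*SAP*

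**What the plan says.** After early termination, SAP 8.3.2 keeps a mean adherence over any treatment duration, a 12-week mean, and the proportions at or above 80% and 90% over 12 weeks. All are descriptive, and all rest on bottle openings.

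- **Numerator (any duration):** "total number of smart bottle openings over the eligible treatment duration excluding the physician-directed interruption periods of the eligible treatment duration", with at most two openings counted per day.
- **Denominator:** two per day of eligible duration, or of 84 days for the 12-week endpoints. The only deduction is "the number of physician-directed interruption days of the eligible treatment duration", with the matching deduction over the first 12 weeks.
- **What is deducted:** "the physician-directed interruption is defined as the reported interruptions due to reasons not being" non-compliance. These are interruptions of dosing.
- **End of the scored interval:** "either the CRF collected date of last dose or the last activity date of smart bottle data, whichever is earlier". A subject needs at least 12 weeks of eligible duration to enter the 12-week endpoints.
- **Device faults:** SAP 8.1 says that "any subject who got a smart bottle with a malfunction signal and never received the alerts", and who was then switched to Arm B, is analysed as a control subject. SAP 7 groups the FAS by technology received, not by randomised arm.
- **Missing data:** SAP 8.1 says that missing data are not imputed unless otherwise specified.

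**The concern.** The bottle opening is the only dosing signal in these endpoints (Protocol 11.3.1). If the bottle stops recording for a period while the subject goes on taking the drug, no dosing interruption has occurred and nothing is deducted. The formula reads the gap as zero openings out of two expected per day, so measurement failure becomes non-adherence. The no-imputation rule does not help, because the formula itself turns absence into zero.

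The SAP also treats silence unevenly. Silence after the last recorded activity is cut off; silence before recording resumes is scored in full. A bottle that fails and is replaced is penalised, while one that fails for good is not.

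At stake are the adherence means and the 80% and 90% proportions. The SAP describes the collected data as limited, so a few affected subjects could move these summaries.

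**Working it through.** **Inputs.** From SAP 8.3.2: two expected openings per day, 84 days, and the deduction and cut-off rules above. From SAP 6.1: SD 8, planned arms of 50 and 25, a difference of 5.6 points, and 80% power. The documents do not give the number of non-recording days *g*, true adherence *a*, or the number of switched subjects *k*; all three are assumptions.

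**The plan's own figure.** A two-sided two-sample t-test with 50 and 25 subjects, SD 8, difference 5.6 and alpha 0.05 has 80.5% power (noncentral t, 73 df), so the stated 80% reproduces. This is context only.

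**Step 1: cost per day, 12-week endpoints.** Expected openings are 2 × 84 = 168. One lost day removes up to 2/168 = 1.19 points. At *a* = 90% it removes 0.90 × 2/168 = 1.07 points.

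**Step 2: effect on one subject.** With no physician-directed interruption, the formula as written gives 100 × *a* × (84 − *g*)/84. With the lost days removed from both parts it gives 100 × *a*.

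| Lost days *g* | *a* = 80% | *a* = 90% | *a* = 95% |
|---|---|---|---|
| 0 (or any *g* after the fix) | 80.0 | 90.0 | 95.0 |
| 3 | 77.1 | 86.8 | 91.6 |
| 7 | 73.3 | 82.5 | 87.1 |
| 14 | 66.7 | 75.0 | 79.2 |
| 28 | 53.3 | 60.0 | 63.3 |

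**Step 3: effect on the cuts.** A subject at 90% falls below 80% once *g* exceeds 84 × (1 − 0.80/0.90) = 9.3, so at 10 days. A subject at 95% falls below 90% once *g* exceeds 84 × (1 − 0.90/0.95) = 4.4, so at 5 days.

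**Step 4: final failure against failure with replacement.** Take *a* = 90%. If recording ends for good on day 40, the eligible duration also ends there. The any-duration value stays at 90%, not 90 × 40/84 = 42.9%, and the subject is left out of the 12-week endpoints. If recording instead stops for 14 of the first 84 days and resumes, the 12-week value is 75.0%.

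**Step 5: effect on the arms, only if openings were lost before a switch.** A switched subject who then uses a recording control bottle has later activity, so a pre-switch gap lies inside the scored interval. With *k* subjects moved at the planned allocation, Arm B has 25 + *k* subjects and its mean falls by 100 × *a* × (*g*/84) × *k*/(25 + *k*). For *k* = 3, *g* = 14 and *a* = 80%, each subject loses 80 × 14/84 = 13.3 points, and 3 × 13.3/28 = 1.4 points.

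The range at *a* = 90%, with no true difference between arms, is:

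| *k* | *g* | A − B, counted in Arm B | A − B, kept in Arm A (n = 50) |
|---|---|---|---|
| 1 | 7 | +0.29 | −0.15 |
| 3 | 14 | +1.61 | −0.90 |
| 5 | 14 | +2.50 | −1.50 |
| 5 | 28 | +5.00 | −3.00 |
| 10 | 28 | +8.57 | −6.00 |

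With *g* = 0, every entry is zero. Regrouping by randomised arm alone changes the sign of the distortion but does not remove it; removing the lost days does.

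**The case against.** The strongest reply is that the malfunction rule concerns alerts, not recording. It describes a malfunction signal and alerts that never arrived. Protocol Table 8-1 shows that the control bottle still sends dosing data to the CRO and the sponsor. A bottle that records but never alerts works like a control bottle, which would explain the rule. This stands: neither document says that openings were lost.

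A reader might infer that device failures collect in the control arm and bias the comparison towards the activated bottle. The documents do not support that. The rule covers only subjects who never received alerts and were switched; any other failure stays in its own arm, and Arm A was planned at twice the size.

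A reader might also point to the dispensing of four bottles, where "Only 1 bottle will be activated at a time", as a second source of lost openings. The protocol does not say that subjects dose from the other bottles or that a non-activated bottle records nothing. The arrangement is the same in both arms, so it gives no reason to expect a difference between them.

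Three further replies stand in part. The last-activity cut-off removes silence after a final failure, but not a gap before recording resumes. The tablet-count and interruption-day compliance in SAP 8.2.6 does not depend on openings, but it is a separate summary and does not correct the bottle endpoints. The analyses are descriptive, so no test is affected; the reported means and proportions still are.

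**Conclusion.** The point holds for gaps in recording between the first dose and the last bottle activity, and within the first 84 days for the 12-week endpoints. On such days the formulas give a wrong value whenever drug was taken, and no other rule corrects it. The size for one subject is up to 1.19 points per day on the 12-week measure.

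Any effect on the comparison of arms is conditional. If openings were lost before a switch, SAP 7 and 8.1 would place that loss in Arm B and favour Arm A. The 1.4-point illustration assumes three switched subjects, 14 lost days each, 80% true adherence and 28 subjects in Arm B. The documents supply none of these as observed values. A smaller Arm B would give a larger shift for the same number of affected subjects; alert-only faults would give none. Bias towards the activated bottle is therefore possible but not shown.

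**What to change.** In both SAP 8.3.2 formulas, remove documented device non-recording days from numerator and denominator, as is already done for physician-directed interruption days. Define what counts as documentation from whatever device or site records exist; neither document describes a device fault log, so its availability should be checked first.

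State how days before a switch to Arm B are scored. List non-recording days by subject, with both randomised and received arm. If no openings were lost, the results do not change and the listing shows that.

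Use the tablet count only as a check over each visit interval. Drug counts are scheduled at Weeks 12, 24, 36 and 48, so each covers about 12 weeks and cannot confirm a gap of one or two weeks.

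The cost is a short SAP change and one listing. The downside is that a few subjects contribute fewer scored days.
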